Patients with electrical and chemical burns will be excluded, as will those with serious inhalation injury requiring treatment to maintain oxygen saturation. Patients in overt shock (defined as serum lactate >2.5 , or hypotension and altered mental status), Pregnant patients, psychiatrically unstable patients will be excluded.

Patients with oropharyngeal defects and/or previously known diagnoses leading to high risk of aspiration, and/or precluding safe nasal-enteric access will be excluded. Patients with history of chronic nausea and/or vomiting, including those with a diagnosis of gastroparesis due to diabetes mellitus will be excluded.

Patients with a Baux score of over 100 (age + TBSA), patients with declared palliative intent on admission, and patients for whom clinicians have high level of clinical concern based on clinical judgement will also be excluded.

Qualitative Component:

Inclusion Criteria

Healthcare workers (physicians, nurses, nursing assistants) who are anticipated to or have provided care to eligible patients in the enteral resuscitation arm of the study.

[figure not shown]
Exclusion Criteria

Exclusion criteria include co-PIs and co-investigators in this study to avoid bias.

11. Intervention

Please see schematic below for Intervention workflow. Specific goal-directed resuscitation protocols for IV fluid resuscitation and Enteral-based resuscitation in **Appendix** including details regarding modifications to allocated interventions based on response, patient request and improving/worsening disease.

Intervention Workflow Overview

General Resuscitation Protocol for Intravenous and Enteral-based Resuscitation

Resuscitation Timeline	Fluid Protocol	Clinical Assessment	Laboratory Assessment*	Additional Interventions
Hour 1	See Appendices A and B	Measure and record vital signs every two hours or more frequently as needed. (Temperature, blood pressure, heart rate, respirations, oxygen saturation), urine output, physical signs of overt shock	CBC, BMP, Lactate, PT/PTT/INR (15 mL)	Additional interventions such as colloid or blood product transfusion, vasoactive agents, escharotomy/ faschiotomy, intubation as deemed necessary by clinical care team will be noted throughout this time period.
Hours 2-7				
Hour 8	Administer Lactated Ringer's (LR) or Oral Rehydration Solution + LR according to calculated Parkland formula**		CBC, BMP, Lactate (10 mL)	
Hours 9-15				

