Hour 16	Add or subtract fluid volume by every 2 hours based on urine output goal of at least 0.5 mL/kg/hr.		CBC, BMP, Lactate (10 mL)	
Hours 16+	IV Metoclopramide to be administered if GI symptoms such as bloating, nausea, discomfort, vomiting.		CBC, BMP, Lactate every 8 hours, and PT/PTT/INR every 24 hours until resuscitation complete.	

* CBC=Complete blood count; BMP=Basic metabolic panel; PT=Prothrombin time; PTT=Partial Thromboplastin time; INR=international normalized ratio

**Parkland formula= $4\text{cc} * \% \text{ Total Body Surface Area burned(TBSA)} * \text{weight(kg)} = 24 \text{ hour fluid volume}$
Total resuscitation volume divided by 2, then divided by 8 to determine the starting resuscitation volume.

12. Outcomes

Goals

The overarching goals are to understand challenges and facilitators of enteral-based resuscitation and understand the effectiveness of the technique compared to standard of care (intravenous resuscitation).

Specific Aim 1: Determine the frequency of adherence to the enteral-based and IV fluid resuscitation protocols, and determine frequency of successful resuscitation.

Hypothesis 1: With goal-directed resuscitation, the primary outcomes of goal average urine output and successful resuscitation will be achieved in the majority of patients (over 50%). Protocol adherence will be at least 50%.

Specific Aim 2: Describe the challenges and facilitators to enteral and IV resuscitation protocol acceptance, implementation, compliance and sustainability.

Hypothesis 2: Enteral resuscitation will have logistical advantages over IV resuscitation, reduce delays in the initiation of resuscitation, have fewer interruptions, and will be easier to implement.

Primary endpoints

For the quantitative aspect, study variables will include measures of implementation and adherence to the enteral resuscitation protocol with variables such as: percent of resuscitation conducted enterally, proportion of protocol laboratory and clinical assessments completed, completeness of bedside documentation, number of inappropriate adjustments of resuscitation fluid rates based on urine output.

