Appendix B: Resuscitation Protocol Flowsheets and Documentation Chart

Enhanced Adult Burn Fluid Resuscitation Protocol for Intravenous Fluid Only Resuscitation

Use for Adults ≥ 18 years, not for pediatric patients, electrical/chemical burn patients or patients with suspected inhalation injury

- Baseline fluid calculation per Parkland Formula ($4\text{cc} \times \% \text{ TBSA} \times \text{weight (kg)} = 24\text{-hour fluid volume}$)
- Vital signs including Heart Rate (HR), Blood Pressure (BP), O₂ saturation and Urine Output (UO) should be tracked every 1 to 2 hours, with fluid rate adjusted accordingly
- **Target Urine Output = 0.5 mL/kg/hr; HR < 120 bpm; Systolic BP >90 mmHg**
- If hypotensive with EITHER Intravenous or enteral-based resuscitation, give bolus of 10cc/kg IV fluids. Consider vasopressor or colloid augmentation.
- For all calculated hourly resuscitation volumes, please round to the nearest 10 (i.e., 74 =70ml, 76=80mL)

[figure not shown]

Adult Burn Fluid Resuscitation Protocol for Enteral-based Resuscitation

Use for Adults ≥ 18 years, not for pediatric patients, electrical/chemical burn patients or patients with suspected inhalation injury

- Vital signs including Heart Rate (HR), Blood Pressure (BP), O₂ saturation and Urine Output (UO) should be tracked every 1 to 2 hours, with fluid rate adjusted accordingly
- Goal: UO=0.5 mL/kg/hr, HR < 120, Systolic BP >90
- If hypotensive with EITHER resuscitation type, give bolus of 10cc/kg IV fluids. Consider vasopressor or colloid augmentation.
- ORS can be administered by drinking or administering the calculated volume via NGT every hour
- For all calculated hourly resuscitation volumes, please round to the nearest 10 (ie 76=80mL)

Abbreviations: IV= Intravenous, RL= Ringer's Lactate, ORS= Oral Rehydration Solution, NGT= Nasogastric Tube

Today's Date: / / 2021			Date and Time of Injury: / / 2021; : AM/PM			InPatient No:							
Name		Admission Wt. (kg)	%TBSA (Do not include superficial 1 st degree burn)			Burn Mechanism							
Parkland Formula: Total Resuscitation Volume: _____ % X _____ kg X 4ml = _____ in 24 hours (TBSA) (pt. weight)						First 8 hours (use 1/2 of total volume) _____ ÷ 8 hrs. Starting Hourly Fluids = _____ ml/hour			Starting 2 Hourly I.V Fluid _____ ml				

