Appendix D: Healthcare Worker Focus Group Interview Guides

Focus Group In-Depth Interview Guides

The following templates outline the anticipated questions that will be used in semi-structured focus group interviews with involved healthcare providers. Based on responses, additional probes and questions may be asked to fully explore the responses.

Physician Focus Group

- Have you previously heard of or personally used Oral Rehydration Solution (ORS)?
- How often do you recommend/prescribe ORS in your typical practice?
 - At Nepal Cleft and Burn Center (NCBC)?
 - In other clinical settings?
- What clinical or laboratory datapoints do you use in your practice to diagnose shock?
- What clinical or laboratory datapoints do you find most useful to assess a patient's resuscitation progress?
- What are challenges with implementation of a resuscitation protocol?
 - Thoughts on hourly check of vitals and urine output
 - Thoughts on hourly adjustments to resuscitation volume
- From your participation in this study and observations made, do you think ORS provides an adequate amount of resuscitation?
- Do you think ORS provides an effective method of resuscitation?
- What are advantages to the use of enteral resuscitation in this population?
- What are challenges in the use of enteral resuscitation in this population?
- Do you think it will be beneficial to implement a protocol for resuscitation?
- After participating in this study, will you plan to increase your use of ORS in your clinical practice with burn patients?
- Do you have additional comments, questions, ideas you would like to offer?
-

Nursing Staff Focus Group

- Have you previously heard of or personally used Oral Rehydration Solution (ORS)?
- How often is ORS used for patients with burn injury at NCBC?
- What signs do you typically first notice when a burn patient starts to get sick?
- What are challenges with implementation of a resuscitation protocol?
 - Thoughts on hourly check of vitals and urine output?
 - Thoughts on adjustments to resuscitation volume?
- From your participation in this study and observations made, do you think ORS provides an effective method of resuscitation?
- What are advantages to the use of enteral resuscitation in this population?
- What are barriers in the use of enteral resuscitation in this population?
- What were logistical difficulties with enteral resuscitation?
- Were there differences in children and adult attitudes towards enteral resuscitation?

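### The primary endpoint names adherence to the enteral protocol only, although Aim 1 covers both arms, and the chart has no labelled field for some scheduled lactates

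*Combined protocol and SAP*

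**What the plan says.** **Aim and hypothesis (Section 12).** Specific Aim 1 is to "Determine the frequency of adherence to the enteral-based and IV fluid resuscitation protocols, and determine frequency of successful resuscitation". Hypothesis 1 adds "Protocol adherence will be at least 50" per cent, without naming an arm, a unit or a denominator.

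**Endpoint (Section 12, Primary endpoints).** The quantitative variables are "measures of implementation and adherence to the enteral resuscitation protocol with variables such as" four examples: the share of resuscitation given enterally, the proportion of scheduled laboratory and clinical assessments done, how complete the bedside record is, and the number of wrong fluid-rate changes given the urine output. The IV protocol is not mentioned.

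**Laboratory schedule (Section 11, General Resuscitation Protocol table).** The table covers both arms. It lists lactate at hours 1, 8 and 16, and after that "CBC, BMP, Lactate every 8 hours, and PT/PTT/INR every 24 hours until resuscitation complete". Sections 13 and 18 also describe laboratory tests as 8-hourly.

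**Documentation Chart (Appendix B).** The laboratory page has seven rows: admission and hours 8, 16, 24, 32, 40 and 48. As printed, CBC and BMP labels appear in all seven. Lactate and coagulation labels appear only at admission, hour 24 and hour 48.

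**Monitoring interval.** The Section 11 table says "Measure and record vital signs every two hours or more frequently as needed". Sections 13 and 18 and the chart rows are also two-hourly. Both Appendix B flowsheets say vital signs and urine output "should be tracked every 1 to 2 hours, with fluid rate adjusted accordingly". A prompt in the Appendix D physician guide reads "Thoughts on hourly adjustments to resuscitation volume".

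**The concern.** Adherence sits under the primary endpoints and has a numerical benchmark. A team that follows the endpoint sentence literally would report adherence for the enteral arm alone. Aim 1 would then be answered for one of its two protocols, and the randomised trial would have no prespecified IV figure to set beside the enteral one. The trial is unblinded, so an IV definition chosen later would be chosen by people who know the allocation and perhaps the results.

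The chart raises a related problem. One listed variable counts scheduled laboratory tests that were done, and Section 18 makes the chart the source document for them. If the chart has no labelled place for a scheduled lactate, an empty cell could mean that the test was not done, or that it was done and not written down. The adherence count cannot tell these apart.

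**Working it through.** **The plan's own figure.** The plan derives no figure for adherence. Its only computed figure is the total of 212 in Section 14, which is for urine output. Inputs are 35% versus 55%, alpha 0.05 (taken as two-sided), power 80% and ratio 1.

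- Mean proportion = (0.35 + 0.55)/2 = 0.45.
- n per arm = [1.960 × √(2 × 0.45 × 0.55) + 0.842 × √(0.35 × 0.65 + 0.55 × 0.45)]² / 0.20² = 96 after rounding up.
- With the continuity correction, n = 106 per arm, or 212 in total.

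This matches the plan and is not affected by the present point.

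**Endpoint scope.** The four listed variables compare with the two arms as follows.

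| Listed variable | Enteral arm | IV arm |
|---|---|---|
| Share given enterally | applies | does not carry over |
| Scheduled assessments done | applies | can be computed |
| Completeness of bedside record | applies | can be computed |
| Wrong fluid-rate changes | applies | can be computed |

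Three of the four are arm-neutral. One schedule table serves both arms, both flowsheets carry the same monitoring line, and the chart has oral and IV fluid columns. The IV measure is therefore available, but the endpoint sentence does not claim it.

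**Lactate fields.** The scheduled times come from the Section 11 table, with hour 1 taken as admission. The labelled fields come from the Appendix B chart.

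- Scheduled through hour 24: admission, 8, 16, 24 = 4. Labelled: admission, 24 = 2. Without a label: 4 − 2 = 2 of 4.
- Scheduled through hour 48: admission, 8, 16, 24, 32, 40, 48 = 7. Labelled: admission, 24, 48 = 3. Without a label: 7 − 3 = 4 of 7.

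The coagulation labels follow the same three times, and these match the 24-hourly coagulation schedule. Such a regular pattern suggests a real feature of the chart, but does not prove it.

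**Effect on overall laboratory completion.** Assume that each scheduled panel counts as one item and that every unlabelled lactate is lost.

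- Through hour 24: 4 CBC + 4 BMP + 4 lactate + 2 coagulation = 14 items, and (14 − 2)/14 = 12/14 = 86%.
- Through hour 48: 7 + 7 + 7 + 3 = 24 items, and (24 − 4)/24 = 20/24 = 83%.

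**Why the 50% needs a referent.** As an illustration, assume that each of 12 two-hourly checks is done independently with probability 0.8. The share of patients called adherent is then P(X ≥ 6) = 99.6%, P(X ≥ 10) = 55.8%, or P(X = 12) = 0.8¹² = 6.9%, depending on the patient-level cut-off. The plan states no cut-off, and does not say whether the 50% refers to patients or to assessments.

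**The case against.** Aim 1 itself commits the team to both protocols, the endpoint list is open-ended, and Section 20 promises description and comparison of the implementation metrics. A sensible analyst would compute IV adherence anyway. This stands against one stronger reading. A reader might infer that Aim 1 cannot be answered for the IV arm, but the shared table, flowsheet wording and chart show that it can. The gap is in what the endpoint specifies, not in what can be measured.

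A reader might also infer that the monitoring passages let one chart pass or fail the 50% benchmark: ten completed rows score 10/12 = 83% against a two-hourly count and 10/24 = 42% against an hourly one. The documents do not support that. Two-hourly appears in Sections 11, 13 and 18 and in the chart rows. The flowsheet range of 1 to 2 hours includes it. Hourly checks and adjustments appear only in interview prompts, which are not a protocol schedule. What remains is a looseness between the flowsheets and the two-hourly passages.

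On lactate, the chart was flattened when read from PDF, and a missing label does not stop a nurse writing a result in the cell. Section 18 also says the chart may be adapted further. These points justify checking the original chart before relying on the count. They do not remove the mismatch as printed.

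Finally, Hypothesis 1 calls urine output and successful resuscitation the primary outcomes, the sample size rests on urine output, and no test is attached to the 50%. The stakes are therefore moderate.

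**Conclusion.** Two inconsistencies hold. First, the aim covers adherence to both protocols and the endpoint sentence covers one, with one of its four variables specific to the enteral arm. Second, as printed, 2 of 4 scheduled lactates through hour 24 and 4 of 7 through hour 48 have no labelled chart field. The second rests on the chart having been read correctly from PDF and on admission being the hour 1 sample.

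The lactate counts should not be read as a ceiling of 50% or 43% on adherence. Those figures arise only if lactate is scored alone, which no section proposes. With all panels pooled, completion would still be 86% or 83%. The flowcharts in Appendix B are not shown, so any further scoring rules there could not be checked. The point is worth fixing before adherence is scored. It does not threaten the sample size or the urine-output comparison.

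**What to change.** 1. In Section 12, change the endpoint to adherence to the allocated protocol, reported in each arm. Use the three arm-neutral variables in both arms and keep the share given enterally for the enteral arm.
2. Have the study team check the original chart and reconcile its laboratory fields with the Section 11 schedule.
3. Have the team reconcile the flowsheet range of 1 to 2 hours with the two-hourly passages.
4. Score both arms against that one reconciled schedule, and state what the 50% applies to: patients or assessments, which arm, and any patient-level cut-off.

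No monitoring interval or laboratory schedule is recommended here; that choice belongs to the study team. The cost is a few sentences in Section 12 and Appendix B and a check of the chart fields. The schedule table and chart already have to serve both arms, so no new data collection is needed to report IV adherence.

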For the qualitative aspect, study variables and themes will be assessed to include the acceptability of the intervention for healthcare workers, acceptability of the intervention for patients, burden of the intervention and protocol for healthcare workers, acceptance of the protocol, perceived knowledge gaps, comfort level with the intervention protocol, concerns with the intervention, favored aspects of the intervention. These study variables will be ascertained from the interview guides, developed using the Consolidated Frameworks for Implementation Research (CFIR).

13. Participant Timeline

Patient screening and enrollment will occur after patient assessment in the Emergency Department at Kirtipur Hospital. After consent and enrollment, randomization to the intervention bundle will occur within the ED.

Treatment will commence per intervention assignment. The patient's clinical status and specific clinical metrics will be assessed every 2 hours during the acute resuscitation period, with laboratory marker measured every 8 hours. The acute resuscitation period typically lasts 24-72 hours.

Within 2 days of completing resuscitation, each patient will undergo a 10-15 minute semi-structured interview with a research assistant regarding their experience and opinion of the resuscitation bundle.

Patients data will be followed for the duration of their inpatient hospitalization in order to track hospital course, and outcomes such as survival and disposition. All communication with the patient and their families will be in person. If the patient and their family opt to do so, they can be contacted after the conclusion of the study with notification of the study results.

14. Sample Size

We would like to update the target patient enrollment to 240 patients. The sample size calculations are demonstrated below, with a necessary sample size of 212 and a 14% increase in target enrollment to account for missing data/dropouts. We assumed an absolute difference in the prevalence of the primary outcome (24-hour UOP within target range) of 20% between the exposed and unexposed, based off of available literature. This is non-probability-based convenience sampling of patients who present with acute burn injuries to Kirtipur Hospital.

Alpha: 0.05 (95% Confidence Level)

Power: 80%

Ratio of unexposed/exposed in sample: 1

Percent of unexposed with outcome: 35%

Percent of exposed with outcome:	Prevalence Difference vs. unexposed	Odds Ratio	Necessary Sample Size

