Trial conduct will be audited by the DSMB when it convenes to review serious adverse events. DSMB members will have access to the collected data to review. There will not be planned in-person audits unless requested by the DSMB members. The DSMB will be independent of study members.

Ethics and dissemination

24. Research Ethics Approval

The study is undergoing ongoing human subjects ethical review by the University of Washington Institutional Review Board and the Nepal National Health Research Council. Institutional approval has been obtained from the phect-NEPAL institutional ethical review board. The study team will work with the above ethical review boards to complete modifications as requested and amend the protocol.

25. Protocol Amendments

Important protocol modifications including changes to eligibility criteria, outcomes and analyses will be communicated to associated Institutional Review Boards (IRB) and trial registries.

Outcomes and analyses will be presented to local and international burn care providers, and manuscripts reflecting the trial outcomes and analyses will be published in local and international journals.

26. Consent or assent

Intervention

Informed consent will be obtained from all patients and/or their authorized surrogate by our research team's trained research assistants after the patient has been identified as eligible for the study on screening and agrees to participate in the study. The consent form will be available in English and Nepali. Please see consent form (Appendix).

For patients who are functionally illiterate, consent will be obtained after understanding and agreement to participate in the study is confirmed by a witness. The patient to be enrolled will provide fingerprint signature, and the witness will sign in the designated area.

Qualitative Component:

Informed consent will be obtained from all participants (doctors, nurses) who participate in the Focus Group Interviews. The consent form will be available in English and Nepali.

All study participants including those from the Intervention and the Qualitative Component will be made aware of their ability to withdraw from the study at any time, and will be instructed in the channels to do so.

27. Confidentiality

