Target Urine Output: _____ kg x 0.5 ml/kg/hr = _____ per hour						Upper CutOff = _____ kg x 0.8 ml/kg/hr = _____ per hr Lower CutOff = _____ kg x 0.2 ml/kg/hr = _____ per hr			2 Hourly Urine Upper Cutoff: _____ ml Target: _____ ml Lower CutOff: _____ ml				
Resuscitation Start time: _____ : _____ AM / PM						Time post Incident: _____ Hrs _____ Mins							
Resus. Hour	Planned total fluid rate	AMOUNT OF FLUIDS GIVEN			Total fluids given (since last check)	Urine Output (q 2hrs)	VITALS		SYMPTOMS: ✓ if yes			Comments on symptoms or issues	CALCULATED RESUSCITATION FOR NEXT 2 HRS.
		Oral fluids		IV fluids			Additional fluids	Heart Rate	Blood Pressure	Oxygen Sat (%)	Nausea		
1 - 2						mL							
3 - 4						mL							
5 - 6						mL							
7 - 8						mL							
9 - 10						mL							
11 - 12						mL							

← Lower Cutoff

TARGET URINE OUTPUT

Upper Cutoff →

↑↑ Fluid by 20%

↑ Fluid by 10%

(continue same)

↓ Fluid by 10%

↓↓ Fluid by 20%

Resus. Hour	Planned total fluid rate	AMOUNT OF FLUIDS GIVEN			Total fluids given (since last check)	Urine Output (q 2hrs)	VITALS			SYMPTOMS: ✓ if yes				Comments on symptoms or issues	CALCULATED RESUSCITATION RATE FOR NEXT 2 HRS.			
		Oral fluids		IV fluids	Additional fluids		Heart Rate	Blood Pressure	Oxygen Sat (%)	Nausea	Vomiting	Distention	Reflux					
		By mouth	By NG															
13 - 14						ml												
15 - 16						ml												
17 - 18						ml												
19 - 20						ml												
21 - 22						ml												
23 - 24						ml												

Resuscitation Laboratory Results

Time of Resuscitation	CBC	BMP	Arterial Blood Gas	Coagulation Markers (PT/PTT/INR)
Admission	WBC: Hgb: Hct: Plt:	Na: K: BUN: Creat:	Lactate: Cl: HCO ₃ :	PT: PTT: INR:
Hour 8	WBC: Hgb: Hct: Plt:	Na: K: BUN: Creat:		
Hour 16	WBC: Hgb: Hct: Plt:	Na: K: BUN: Creat:		
Hour 24	WBC: Hgb: Hct: Plt:	Na: K: BUN: Creat:	Lactate: Cl: HCO ₃ :	PT: PTT: INR:
Hour 32	WBC: Hgb: Hct: Plt:	Na: K: BUN: Creat:		
Hour 40	WBC: Hgb: Hct: Plt:	Na: K: BUN: Creat:		
Hour 48	WBC: Hgb: Hct: Plt:	Na: K: BUN: Creat:	Lactate: Cl: HCO ₃ :	PT: PTT: INR:

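### One of the listed adherence variables is a raw count of inappropriate fluid-rate adjustments with no denominator or window, so at equal adherence it varies threefold with length of resuscitation

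*Combined protocol and SAP*

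**What the plan says.** Section 12 (Outcomes), under Primary endpoints, gives an open list of implementation and adherence measures. Three are introduced as "variables such as: percent of resuscitation conducted enterally, proportion of protocol laboratory and clinical assessments completed, completeness of bedside documentation". The fourth is the "number of inappropriate adjustments of resuscitation fluid rates based on urine output". The first three are a percent, a proportion and a completeness measure; the fourth is a number.

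Specific Aim 1 in the same section is to "Determine the frequency of adherence to the enteral-based and IV fluid resuscitation protocols", and Hypothesis 1 states "Protocol adherence will be at least 50" per cent. Section 13 (Participant Timeline) says that "specific clinical metrics will be assessed every 2 hours during the acute resuscitation period" and that "The acute resuscitation period typically lasts 24-72 hours".

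The Documentation Chart in Appendix B has one row per 2 hours. Each row ends in a column headed "CALCULATED RESUSCITATION FOR NEXT 2 HRS" (the second page words it slightly differently). A key maps urine output to five responses: raise the rate by 10% or 20%, leave it as it is, or lower it by 10% or 20%. The printed rows stop at hours 23-24.

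Section 26 tells participants of their "ability to withdraw from the study at any time", and Section 22 lists death among the serious adverse events. Neither says what happens to the count after such an event. Section 20 (Statistical Methods) promises description and comparison of the implementation metrics in general terms, with no rate or per-decision analysis.

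**The concern.** A count of errors depends on how often errors are made and on how many chances there were to make one. Here the number of chances differs between patients by design, because resuscitation lasts as long as it needs to and can be cut short. The count therefore mixes adherence with time on protocol: a long, well-run resuscitation can score worse than a short, poorly run one.

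Two further problems follow. Aim 1 asks for a frequency and Hypothesis 1 sets a percentage, and a count supplies neither. And the phrase refers to adjustments, so a rate left unchanged when the chart calls for a change is, on a literal reading, not recorded as an error.

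What is at stake is the meaning of one measure listed as primary. If time on protocol differs between groups, a difference in exposure could be read as a difference in adherence.

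**Working it through.** **The plan's own figure.** The documents give no expected value, spread or power for the count. The only stated calculation is the total of 212 in Section 14, for 24-hour urine output in range, 35% versus 55%, alpha 0.05, power 80%, ratio 1. Two-sided, with mean proportion 0.45:

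- n0 = [1.960 × √(2 × 0.45 × 0.55) + 0.842 × √(0.35 × 0.65 + 0.55 × 0.45)]² / 0.20² = 95.9 per arm.
- With continuity correction, n = (n0/4) × [1 + √(1 + 4/(n0 × 0.20))]² = 105.7, so 106 per arm and 212 in total.

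This reproduces the stated figure. It rests on urine output and not on adherence, so nothing below changes it.

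**Inputs for the count.**

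- Decision interval: 2 hours (Section 13 and the chart).
- Duration: 24 to 72 hours (Section 13).
- Error rate per decision, q: not in the documents; assumed 10% to 50%.
- An early end at hour 8: assumed, for illustration only.
- Share of checks that call for a rate change: not in the documents; assumed 45% to 65%.

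**Step 1: decisions.** Decisions = hours / 2, so 24/2 = 12, 48/2 = 24 and 72/2 = 36. The assumed early end gives 8/2 = 4.

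**Step 2: expected count at equal adherence.** Expected count = q × decisions.

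| q (assumed) | 8 h (assumed) | 24 h | 48 h | 72 h |
|---|---|---|---|---|
| 10% | 0.4 | 1.2 | 2.4 | 3.6 |
| 20% | 0.8 | 2.4 | 4.8 | 7.2 |
| 30% | 1.2 | 3.6 | 7.2 | 10.8 |
| 50% | 2.0 | 6.0 | 12.0 | 18.0 |

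The ratio of 72 h to 24 h is (q × 36)/(q × 12) = 3 for every q. It does not depend on the interval either. Appendix B allows tracking every 1 to 2 hours; hourly decisions would give 72/24 = 3.

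**Step 3: the same count at different lengths.** Three inappropriate decisions are 3/4 = 75% of those due at 8 h (assumed), 3/12 = 25% at 24 h and 3/36 = 8.3% at 72 h. The count alone cannot tell these apart, so it cannot be placed above or below 50% adherence.

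**Step 4: required changes not made.** Take a team that never alters the rate. If only changes actually made are scored, the count is 0. If omissions are scored, it is 12 × 0.45 = 5.4 to 12 × 0.65 = 7.8 in 24 h, and 36 × 0.45 = 16.2 to 36 × 0.65 = 23.4 in 72 h. The documents do not say which rule applies.

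**Step 5: the proportion.** Dividing by decisions due gives an expected value of (q × decisions)/decisions = q at every duration. The dependence on length disappears if q is steady over time. If q drifts during resuscitation, a fixed window limits what remains.

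**The case against.** The strongest reply is that this is one example in an open list, that the other three measures are already scaled, and that the count may never have been meant to run past the chart. The chart's printed 2-hourly rows end at hour 24, and the outcome in Section 14 is 24-hour urine output. If the count were taken only from those rows, every patient who reaches hour 24 would have 12 decisions, and the threefold range would largely vanish for them. That is fair as far as it goes. But no section states such a window, Section 13 keeps 2-hourly assessment going throughout resuscitation, and patients who end before hour 24 would still differ.

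Some of the Appendix B flowsheets are not reproduced in the text available here and may hold more detail on when a change is required. That could help to define an inappropriate adjustment, but a clinical flowsheet would not be expected to supply a denominator.

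A reader might infer several stronger things that the documents do not support:

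- That adherence as a whole rests on this count. It is one of four example variables, and no cut-off turns it into good or poor adherence.
- That never adjusting is scored as good adherence. That is the literal reading, but inappropriate is undefined. Because leaving the rate alone is itself one of the chart's responses, a missed change could also be scored as an error.
- That the range is much wider than threefold. This needs an exit within a few hours, for which the documents give no frequency, and the exclusions in Section 10 (overt shock, Baux score over 100, palliative intent) make very early death less likely.
- That the comparison between arms is biased. That needs duration or early ending to differ by arm. It is possible in an open-label trial, but the documents give no figure for it.

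**Conclusion.** The point holds for this one variable. On the plan's own figures of 2-hourly decisions and 24 to 72 hours, the expected count varies threefold at identical adherence. That ratio needs no assumed error rate, only an error rate that is the same across durations and a count that runs for the whole resuscitation. The count falls further when resuscitation ends early, by an amount that the documents do not allow to be estimated. It cannot be compared with the 50% in Hypothesis 1, and whether omissions count is left open.

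This goes beyond missing detail, because the measure as worded depends on exposure and a better one can be built from the same chart. It should be corrected, but it does not threaten the sample size or the urine output outcome, and no bias between arms has been shown.

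**What to change.** In Section 12, replace the count with a proportion, derived identically in both arms:

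- **Numerator:** 2-hourly rate decisions handled as the Documentation Chart requires, including leaving the rate unchanged where the chart says so.
- **Denominator:** 2-hourly decisions due while the patient is under protocol resuscitation, in the first 24 hours. This matches the chart's printed rows and the 24-hour urine output outcome.
- **Non-adherent:** a required change that was not made, or a due decision left uncharted while on protocol.
- **Early ends:** stop the denominator at death, withdrawal or completed resuscitation, so that decisions nobody could make are not counted as due. Report the number of early ends and the reasons by arm beside the proportion.
- **Change of route:** keep counting decisions after a patient in the enteral arm moves to IV fluid.

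This changes measurement only; it leaves the chart's clinical rules as they are. The cost is a wording change in Section 12 and one derived variable in REDCap. Urine output, planned rate, fluids given and the calculated next rate are already charted 2-hourly for the first 24 hours. There are two drawbacks. Stated adherence may look lower, because missed changes and blank rows now count against it. And the measure says nothing about decisions after hour 24. The sample size of 212 does not change.
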